#### 2.3.3. Overall Benefit: Risk Conclusion

ALXN1830 was well tolerated after single doses up to 30 mg/kg IV and 1250 mg SC (the highest single doses tested in SAD studies) in healthy adults. Also, ALXN1830 was well tolerated after multiple IV doses at 10 mg/kg × 5 doses in autoimmune patients. However, at multiple IV doses of 20 mg/kg in healthy participants, the development of potentially immune mediated IRRs that resulted in immediate and permanent discontinuation of study drug, together with 100% incidence rate of headache, suggested that close safety monitoring and implementation of risk mitigation measures are warranted for future studies in the clinical development program (Section 10.6). Of note, these IRRs were mild and moderate in severity and all resolved after cessation of the study drug, without treatment. Similarly, all AEs of headache were mild to moderate and were resolved.

As described in Section 2.1, potential impurities in the drug product could possibly have confounded the safety profile. Alexion has implemented changes to the manufacturing process for the current and future batches to enhance the control and detection of impurities.

The proposed safety measures in this study include documentation of pneumococcal and current seasonal flu vaccination; staggered dosing; stopping rules; close participant monitoring through 60 days after the last dose; close safety and PD monitoring with an unblinded medical monitor; avoidance of participants with a high risk of infections; antibiotics to manage infection as needed; rescue measures such as IVIG replacement in an extremely unlikely event of profoundly low IgG; as well as use of an SRC for safety monitoring and dose selections.

Considering the measures taken to minimize risk to participants in this study, the risks associated with ALXN1830 are justified by the anticipated benefits that may be afforded to patients with autoimmune disease.

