An SRC, consisting of the Investigator, and Alexion Safety Physician, Medical Monitor, Study Statistician, and Clinical Pharmacologist, will evaluate the study data at prespecified time points for participant safety and make recommendations on dose escalation, dose modification, or termination of the study (see SRC charter for description of membership, schedule of meetings, data required for each safety review, and requirements for documenting meeting discussions and outcome). Relevant safety data from any other studies ongoing with ALXN1830 will be made available to the SRC. At Alexion's discretion, and after consultation with the SRC, additional participants may be enrolled as replacement participants only if a participant discontinues within 3 weeks of the last dose for reasons other than drug-related AEs.

The timing and dependencies of the dosing cohorts are described in Table 14 and Table 15.

Table 14: Planned Dose and Dose Regimens of ALXN1830 in Healthy Participants

Cohort No.	Regimen/Route of Administration	Study Drug (N)
1	Single dose SC	Placebo (n = 2) or
		$ALXN1830\ 1500\ mg\ (n=6)$
2	Single dose SC	Placebo $(n = 2)$ or
		ALXN1830 2250 mg (n = 6)
3	Multiple dose (12 doses qw) SC	Placebo $(n = 2)$ or
		ALXN1830750  mg  (n = 6)
4	Multiple dose (4 doses qw) SC	Placebo $(n = 2)$ or
		ALXN1830 1500  mg  (n = 6)
5	Multiple dose (4 doses qw) SC	Placebo $(n = 2)$ or
	-	ALXN1830 2250 mg (n = 6)
6 a	Multiple dose (4 doses qw) SC	Placebo (n = 2) or
	Japanese healthy participants	ALXN1830 HTD (n=6)

<sup>a Healthy, Japanese participants enrolled in Cohort 6 will be dosed according to the HTD established in the non-Japanese cohorts.

Abbreviations: qw = weekly; SC = subcutaneous; HTD = highest tolerated dose.

**Table 15:** Minimum Data Requirements for Dose Escalation

Decision- making Time Point:	Dosing Regimen	Person or Body Making the Decision:	Minimum Data to be Looked at (in Accordance With the CSP):	Method of Documentation of Decision and/or Communication to Alexion (if Applicable):
Continuation from any sub-cohort to the next sub- cohort, within any cohort	As per relevant cohort	ΡΙ	A minimum of 3 days (SAD) / 7 days (MAD) post-dose safety and tolerability data from the first sub-cohort.	The Investigator will document the decision in an email to Alexion. The email does not require Alexion's response, unless there is disagreement with the Investigator's decision.
Cohort 1	1500 mg, single dose SC	N/A	N/A	N/A

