Cohort 2	2250 mg, single dose SC	SRC	Review all available safety data and IgA, IgG, and IgM data through Day 15 from Cohort 1, from a minimum of 6 participants.	The SRC will document the decision on the escalation/progression approval form.
Cohort 3	750 mg, 12 doses SC, once weekly	SRC	N/A This cohort may start in parallel to Cohort 1.	N/A
Cohort 4	1500 mg, 4 doses SC, once weekly	SRC	Review all available safety data and IgA, IgG, and IgM data through Day 22 from Cohort 3, from a minimum of 6 participants.	The SRC will document the decision on the escalation/progression approval form.
Cohort 5	2250 mg, 4 doses SC, once weekly	SRC	Review all available safety data and IgA, IgG, and IgM data through Day 22 from Cohort 4, from a minimum of 6 participants.	The SRC will document the decision on the escalation/progression approval form.
Cohort 6 a	HTD, 4 doses SC, once weekly	SRC	Review all available safety data and IgA, IgG, and IgM data through Day 22 from Cohort 5.	The SRC will document the decision on the escalation/progression approval form.

<sup>a Healthy, Japanese participants enrolled in Cohort 6 will be dosed according to the HTD established in the non-Japanese cohorts.

Abbreviations: CSP = Clinical Study Protocol; HTD = highest tolerated dose; Ig = immunoglobulin; MAD = multiple ascending dose; N/A = not applicable; PI = Principal Investigator; PK = pharmacokinetics; SAD = single ascending dose; SC = subcutaneous; SRC = Safety Review Committee.

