## 4.2. Scientific Rationale for Study Design

ALXN1830 has been studied in 5 clinical studies, 4 studies using the IV route of administration and one SC administration. Refer to Section 2.2 for background on clinical studies conducted with ALXN1830 to date.

This randomized, double-blind, PBO-controlled, SAD/MAD design was chosen for assessment of the safety, tolerability, PK/PD, and immunogenicity of single- and multiple ascending doses of ALXN1830 administered SC.

Healthy participants are the appropriate population for this study, enabling the effects of ALXN1830 to be evaluated without the potential confounding effects of other disease activities, comorbidities, or medications.

A staggered dosing paradigm is being used for participant protection. A PBO control is implemented in each cohort. Due to the difficulty of providing a matching PBO, participants randomized to PBO will receive an equivalent volume of saline at the same SC infusion rate as the active treatment.

ALXN1830 is an anti-FcRn mAb that blocks recycling of IgG antibodies, reducing the total IgG in circulation, including potentially pathogenic IgG autoantibodies associated with multiple autoimmune diseases. Thus, reduction in IgG level is used to measure the anti-FcRn PD activity of ALXN1830.

This study uses a comprehensive approach to minimize the potential risk of infection in the healthy participants due to the theoretical concerns associated with reducing total IgG (discussed in greater detail in Section 10.6). The following criteria will be observed as part of the enrollment criteria (Section 5.1), monitoring, and specified response to certain signs, symptoms, or laboratory results:

- Inclusion criteria of heathy participants with:
  - Immunoglobulin G levels of  $\geq 1,000 \text{ mg/dL}$
  - No history of acute and chronic infections, ie, enrolled healthy participants will be immunocompetent
  - Absence of any immunologic deficiencies, as per the Investigator's discretion
  - Pneumococcus and seasonal influenza vaccination
- To ensure a timely and adequate intervention if needed, IgG levels will be continuously and closely monitored during this study.
- Stopping rules (Section 7.2) for individuals and cohorts will be based on reduction of IgG level to ≤ 300 mg/dL (justification for IgG level to ≤ 300 mg/dL is provided in Section 10.6).
  - Dosing will be permanently stopped in any individual if the IgG level is reduced to ≤ 300 mg/dL.

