  - If 2 or more participants in a cohort exhibit an IgG reduction to ≤ 300 mg/dL, dosing in that cohort will stop and no further dose escalation will occur.

• Although unlikely to occur, in the unexpected instance of an IgG reduction falling into the severe category (ie, less than 100 mg/dL) or if there is any suggestion, signs, or symptoms of infection, antibiotics and/or IVIG will be considered.

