# 7.2. Stopping Criteria

#### 7.2.1. Immunoglobulin Stopping Rules

It is proposed that the lower limit of IgG will be set at  $\leq 300$  mg/dL as an individual stopping rule for the healthy participant study. More specifically, if any predose measurements show a reduction of IgG level to  $\leq 300$  mg/dL, the individual stopping rule will be met. Repeat testing to confirm the consistency of the result is permitted. Healthy participants can rebound to their baseline IgG level when the drug is discontinued because they are not immunocompromised, as evidenced by existing anti-FcRn studies. Additionally, risk mitigation strategies such as antibiotics or IVIG replacement therapy may be implemented if participants have laboratory evidence of infection and/or are clinically symptomatic.

If 2 or more participants in a cohort exhibit IgG reduction to  $\leq 300 \text{ mg/dL}$ , dosing in that cohort/dose level will stop and no further dose escalation will occur.

In addition, any participant for whom IgA or IgM falls below the normal limits (according to the reference ranges of the laboratory) and is associated with clinical signs and symptoms will be discontinued from further dosing.

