#### **Cohort and Study Level:**

- A cohort and other cohort with a dose at an equal or higher level will be stopped or not initiated if any of the following occurs:
  - 2 participants on study drug in the cohort experience a moderate (Grade 2) AR
     that does not improve by 14 days after treatment
  - $\geq$  2 participants on study drug in the cohort experience an IRR as described earlier (see individual level)
- Study will be discontinued (all dosing [lower, equal, or higher doses]) and continuation of the cohort or study will require a substantial amendment, if any of the following occurs:
  - Two participants on study drug in any cohort experience a severe (Grade 3) AR
  - One participant on study drug in any cohort experiences a serious AR

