### 10.7.1.1. IgG Level Stopping Rule

The stopping rule based on IgG level of  $\leq$  300 mg/dL was chosen based on generally used classifications of IgG lowering and the prior experience with anti-FcRn treatments discussed above. Classification of reduction in IgG levels has been specified as "mild to moderate" (300 to 600 mg/dL), "significant" (100 to 299 g/dL), or "profoundly reduced" ( $\leq$  100 mg/dL).

Participants with IgG levels of 200 to 400 mg/dL and total Ig level of 400 to 600 mg/dL are considered to have adequate antibody levels to convey humoral immunity, but this is less likely if total Ig levels are less than 400 mg/dL or serum IgG levels are less than 200 mg/dL (Agarwal and Cunningham-Rundles, 2007). Prior experience with anti-FcRn therapeutics in healthy participants showed no increased risk of evidence of infection despite reduction in IgG less than 200 mg/dL. Thus, isolated reduction of IgG to levels as low as 200 mg/dL in the presence of normal IgA and IgM levels and normal cellular elements of immunity (white blood cell [WBC]/differential) would most likely maintain an immunocompetent status. However, to avoid IgG reductions below the mild to moderate range, we will utilize a more conservative level of 300 mg/dL as the threshold for individual and cohort level stopping rules.

To further ensure the IgG nadir would not drop below 300 mg/dL, the inclusion criterion for IgG was set to  $\geq 1000$  mg/dL, higher than the lower limit of normal. Since the proposed dosing regimens of ALXN1830 are not expected to lower IgG levels more than  $\sim 70\%$  as predicted by PK/PD modeling, the IgG levels should remain above 300 mg/dL. Furthermore, the IgG nadir is a transient phenomenon, with IgG levels rising back towards baseline in a relatively rapid timeframe.

Finally, IVIG replacement will be considered only if IgG is profoundly low, ie, below 100 mg/dL, and this low nadir is sustained for more than 7 days despite discontinuation of ALXN1830, which again would be an extremely unlikely event as discussed above.

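### The cohort-level IgG stopping rule does not automatically reach a higher multiple-dose cohort that is already dosing

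*Protocol*

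**What the plan says.** **The IgG rule.** Protocol section 7.2.1 stops an individual whose predose IgG is 300 mg/dL or lower; section 4.2 makes that stop permanent. If two or more participants in one cohort reach that level, 7.2.1 says "dosing in that cohort/dose level will stop and no further dose escalation will occur". Section 4.2 repeats this for the cohort alone: "dosing in that cohort will stop and no further dose escalation will occur". On the threshold, section 10.7.1.1 says "we will utilize a more conservative level of 300 mg/dL as the threshold for individual and cohort level stopping rules".

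**The reaction rule.** For adverse reactions and infusion-related reactions, section 7.2.2 reaches further: "A cohort and other cohort with a dose at an equal or higher level will be stopped or not initiated".

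**The gates.** In Table 15 (section 4.1), the SRC's minimum for opening Cohort 4 is "Review all available safety data and IgA, IgG, and IgM data through Day 22 from Cohort 3, from a minimum of 6 participants". Moving from one sub-cohort to the next is the Investigator's decision, and the stated minimum is "A minimum of 3 days (SAD) / 7 days (MAD) post-dose safety and tolerability data from the first sub-cohort".

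**Monitoring.** Section 4.2 says "IgG levels will be continuously and closely monitored during this study", and section 2.3.3 lists "close safety and PD monitoring with an unblinded medical monitor" among the safety measures (also in section 10.7). Section 6.6 leaves dose decisions to the Investigator and/or the SRC on blinded data.

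**The concern.** The IgG rule treats a trigger as a reason not to go higher. Its wording covers the cohort or dose level that triggered and any escalation still to come. It does not mention a higher-dose cohort that opened before the trigger. Read literally, a late trigger in Cohort 3 stops 750 mg weekly and leaves participants already on 1500 mg weekly to continue.

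The two cohorts share a basis for prediction. Section 4.3 says no subcutaneous PK/PD model was yet available, and Table 16 takes its IgG predictions from equivalent intravenous doses: maximum falls of 68%, 69% and 72% for Cohorts 3, 4 and 5. Section 10.7.1.1 relies on falls of no more than about 70% to keep IgG above 300 mg/dL. Two Cohort 3 participants at or below 300 mg/dL would call that expectation into question for the higher doses too. These are healthy participants with no direct benefit, so a prompt look at the higher cohort is worth securing in the text.

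**Working it through.** The protocol gives no figure to reproduce. The check is a dosing calendar, then the remaining exposure, then what a trigger requires.

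**Inputs.** Cohort 3: 12 weekly doses. Cohorts 4 and 5: 4 weekly doses each. Each cohort starts with 4 participants (3 active, 1 placebo), then the other 4 (again 3 active, from the 6:2 ratio) at least 7 days later (section 4.1). The Cohort 5 gate mirrors that for Cohort 4. Assumption: L is the number of days from the last required Day 22 sample to the next cohort's first dose. The text does not give L, so it is varied.

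**Calendar, at the minimum 7-day stagger (day 1 = first Cohort 3 dose).**
- Cohort 3 doses run on days 1 to 78 (first sub-cohort) and 8 to 85 (second).
- Six participants require the second sub-cohort, whose Day 22 is calendar day 22 + 7 = 29.
- Cohort 4 doses on days 29+L to 50+L, then 36+L to 57+L.
- Cohort 4 overlaps Cohort 3 dosing if 29 + L ≤ 85, so L ≤ 56.
- Cohort 5 starts on day 57 + 2L, with the same lag at both reviews. It overlaps if 57 + 2L ≤ 85, so L ≤ 14.

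**Trigger opportunities.** Tables 4 to 8 give predose IgG after the first dose on Days 8, 15, 22, 29, 36, 43, 50, 57, 64, 71 and 78, which is 11. Three are in the minimum data that open Cohort 4; 11 − 3 = 8 come later. The window from day 29+L up to, but not including, day 57+L lasts 28 days, so for L of 1 to 28 it holds 28/7 = 4 checks per Cohort 3 participant.

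**Exposure ahead at 1500 mg.** Cohort 4 has 6 × 4 = 24 active infusions. Those still ahead for participants already dosed, counted after that day's infusions, are:

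| Trigger on Cohort 4 day | First sub-cohort | Second sub-cohort | Total |
|---|---|---|---|
| 1 | 3 × 3 = 9 | not yet dosed | 9 |
| 8 | 3 × 2 = 6 | 3 × 3 = 9 | 15 |
| 15 | 3 × 1 = 3 | 3 × 2 = 6 | 9 |
| 22 | 0 | 3 × 1 = 3 | 3 |

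These are upper bounds. They ignore the mandatory individual stop and any SRC or Investigator action.

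**What a trigger requires.** The fall needed is 1 − 300/baseline: 70% at the eligibility floor of 1,000 mg/dL and 75% at 1,200 mg/dL. The baseline at which the predicted maximum fall gives 300 mg/dL is 300/(1 − fall):
- Cohort 3: 300/0.32 = 938 mg/dL
- Cohort 4: 300/0.31 = 968 mg/dL
- Cohort 5: 300/0.28 = 1,071 mg/dL

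Only the Cohort 5 prediction reaches the limit within the eligible range.

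**Likelihood.** A probability needs the between-participant spread and the baseline distribution, and the documents give neither. If Cohort 3 falls are taken as normal with mean 68% and an assumed SD of 3 to 8 points, and all baselines are set to one value between 1,000 and 1,200 mg/dL, the chance that at least 2 of 6 active participants reach 300 mg/dL runs from 0.001 to 0.77. The assumptions decide the answer. The calculation also uses maximum rather than predose falls and does not exclude triggers by Day 22, so it is not evidence of likelihood.

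**The case against.** The case for leaving the rule alone is substantial.

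- **The SRC may act anyway.** Section 9.6 sends the SRC's meeting schedule and data requirements to a charter that is not among the documents, and it may contain such a rule. A trigger bars escalation, and the SRC decides each gated escalation, so it would very probably be involved. This stands as a practical point, but the protocol states no notification step or hold.
- **Symptomatic cases are covered.** A drug-related infection would be an adverse reaction. Under 7.2.2, two Grade 2 reactions not improving by 14 days stop cohorts at an equal or higher dose, and one serious reaction stops all dosing. This stands: the uncovered case is mainly an asymptomatic laboratory value.
- **IgG differs from reactions.** Its fall is the intended, reversible drug effect and is measured before each weekly dose (Table 11 for Cohort 4). Cohort 4's own values are the most direct evidence about Cohort 4, and a late Cohort 3 trigger may reflect 12 weeks of dosing rather than dose. This argues against a permanent stop; it does not argue against a hold for review.
- **A trigger is not predicted in Cohort 3.** The 938 mg/dL figure is below the eligibility floor, and the largest fall reported so far with this drug was 64% (section 10.7.1). This stands.

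A reader might infer that Cohort 4 would have no IgG protection, or that its undosed second sub-cohort could start after a Cohort 3 trigger. The documents support neither. The individual stop and Cohort 4's own trigger apply throughout. The bar on further escalation is naturally read to cover people not yet dosed at 1500 mg, although the sub-cohort row of Table 15 does not say so.

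**Conclusion.** The gap is real in the protocol text and limited in consequence. No stated rule links an IgG trigger in a lower multiple-dose cohort to a higher cohort already dosing, and Table 15 permits that overlap for Cohort 4 at any review lag up to 56 days. What is missing is an automatic hold and review of the higher cohort. Each Cohort 4 participant is still stopped on their own value, and section 10.7.1.1 considers an isolated fall to 200 mg/dL most likely compatible with immunocompetence.

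The calendar assumes the minimum stagger. A reader might take the 9, 15, 9 and 3 infusions as expected excess exposure, or take a trigger as likely. The first are ceilings that set aside a mandatory rule; for the second the documents give no basis. SAP section 4.1 records early termination, which does not change how the rule reads. The change is worth making as a cheap safety improvement, but the gap does not show that the trial was unsafe.

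**What to change.** Keep the existing sentence in 7.2.1 whole, including its reference to the dose level and its bar on escalation. Undosed sub-cohorts and cohorts at a higher dose then stay closed, rather than being put on a reviewable hold. Add to 7.2.1 and 4.2:

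> *Dosing of participants already receiving a higher dose level in another multiple-dose cohort will be held pending SRC review.*

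In the sub-cohort row of Table 15, add the condition that no IgG cohort trigger is in force at an equal or lower multiple-dose level.

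The change needs no new samples, visits or participants. Its cost is that Cohort 4 or 5 dosing may be delayed or cut short, including after a late Cohort 3 trigger that reflects duration rather than dose.

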# 7.2.2. Safety Stopping Rules (Individual, Cohort and Study Level Stopping Rules) Individual Level:

- Study drug will be discontinued immediately (if applicable) and permanently if any of the following occurs:
  - Development of a 'serious' adverse reaction (AR), or 'severe' (≥ Grade 3) AR.
  - Development of a 'serious' adverse reaction (AR), or 'severe' (≥ Grade 3) IRR.
- If a moderate Grade 2 AR is observed, study drug administration may be continued, delayed, or discontinued in accordance with Investigator's clinical judgment and in consultation with Alexion.

#### **Cohort and Study Level:**

- A cohort and other cohort with a dose at an equal or higher level will be stopped or not initiated if any of the following occurs:
  - 2 participants on study drug in the cohort experience a moderate (Grade 2) AR
     that does not improve by 14 days after treatment
  - $\geq$  2 participants on study drug in the cohort experience an IRR as described earlier (see individual level)
- Study will be discontinued (all dosing [lower, equal, or higher doses]) and continuation of the cohort or study will require a substantial amendment, if any of the following occurs:
  - Two participants on study drug in any cohort experience a severe (Grade 3) AR
  - One participant on study drug in any cohort experiences a serious AR

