# 7.4. Lost to Follow-up

A participant will be considered lost to follow-up if he or she repeatedly fails to return for scheduled visits and is unable to be contacted by the study site.

The following actions must be taken if a participant fails to return to the clinic for a required study visit:

- The site must attempt to contact the participant and reschedule the missed visit as soon as possible and counsel the participant on the importance of maintaining the assigned visit schedule and ascertain whether the participant wishes to and/or should continue in the study.
- Before a participant is deemed lost to follow-up, the Investigator must make every
  effort to regain contact with the participant (where possible, 3 telephone calls and, if
  necessary, a certified letter to the participant's last known mailing address or local
  equivalent methods). These contact attempts should be documented in the
  participant's medical record.

• Should the participant continue to be unreachable, he/she will be considered to have withdrawn from the study.

Discontinuation of specific sites or of the study is handled as part of Section 10.1.9 Study and Site Start and Closure.

The Investigator, competent authority, or Sponsor may terminate the study for reasonable cause. Conditions that warrant termination of the study include, but are not limited to, the following:

- Discovery of an unexpected, serious, or unacceptable risk to participants enrolled in the study.
- Decision on the part of Alexion to suspend or discontinue testing, evaluation, or development of the study drug.
- Failure of the Investigator to comply with the approved protocol, pertinent guidelines, and/or regulations.
- Submission of knowingly false information from the Investigator to Alexion and/or regulatory authorities.

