#### 8. STUDY ASSESSMENTS AND PROCEDURES

- Study procedures and their timing are summarized in the SoA (Section 1.3). Protocol waivers or exemptions are not allowed.
- Immediate safety concerns should be discussed with Alexion immediately upon occurrence or awareness to determine if the participant should continue or discontinue study drug.
- Adherence to the study design requirements, including those specified in the SoA, is essential and required for study conduct.
- All screening evaluations must be completed and reviewed to confirm that potential
  participants meet all eligibility criteria. The Investigator will maintain a screening log
  to record details of all participants screened and to confirm eligibility or record
  reasons for screening failure, as applicable.
- Procedures conducted as part of the participant's routine clinical management (eg, blood count) and obtained before signing of the ICF may be utilized for screening or baseline purposes provided the procedures met the protocol-specified criteria and were performed within the time frame defined in the SoA.

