#### 4. Results in persistent disability/incapacity

- The term disability means a substantial disruption of a person's ability to conduct normal life functions.
- This definition is not intended to include experiences of relatively minor medical significance such as uncomplicated headache, nausea, vomiting, diarrhea, influenza, and accidental trauma (eg, sprained ankle) which may interfere with or prevent everyday life functions but do not constitute a substantial disruption.

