#### **Assessment of Intensity**

The Investigator will make an assessment of intensity for each AE and SAE reported during the study and assign it to one of the following categories from National Cancer Institute CTCAE v5.0, published 27 Nov 2017:

- Grade 1: Mild (awareness of sign or symptom, but easily tolerated)
- Grade 2: Moderate (discomfort sufficient to cause interference with normal activities)
- Grade 3: Severe (incapacitating, with inability to perform normal activities)
- Grade 4: Life-threatening
- Grade 5: Fatal

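### The cohort stopping trigger counts only Grade 2 adverse reactions, so one persistent Grade 2 plus one persistent non-serious Grade 3 reaction triggers no mandatory stop, while two persistent Grade 2 reactions do

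*Protocol*

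**What the plan says.** Protocol Section 7.2.2 sets two mandatory triggers at cohort level and two at study level.

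- **Cohort, AR:** "2 participants on study drug in the cohort experience a moderate (Grade 2) AR", with the condition that the AR has not improved by 14 days after treatment. That cohort, and others at an equal or higher dose, are then stopped or not started.
- **Cohort, infusion-related reaction (IRR):** two or more participants with an IRR of the kind in the individual-level rule, that is, serious or Grade 3 and above.
- **Study, Grade 3:** "Two participants on study drug in any cohort experience a severe (Grade 3) AR".
- **Study, serious:** one participant with a serious AR.

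At individual level, study drug is stopped permanently for "Development of a 'serious' adverse reaction (AR), or 'severe' (≥ Grade 3) AR". A Grade 2 AR is left to the Investigator in consultation with the sponsor.

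Section 10.3.3 keeps Grades 2 and 3 as separate categories. It describes the upper one as "Grade 3: Severe (incapacitating, with inability to perform normal activities".

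**The concern.** A stopping rule should not become weaker as events become worse. Here it does for one pair. Two persistent Grade 2 ARs oblige the cohort to stop. If one of them is replaced by a non-serious Grade 3 AR that also fails to improve, the obligation disappears, because the two events fall in different counts and each count reaches only one.

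What is at stake is whether the other participants in that cohort, and cohorts at equal or higher doses, are protected by a fixed rule or only by judgement. This matters mainly in the multiple-dose cohorts, where dosing can still be under way when the 14 days have passed.

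**Working it through.** The plan states no operating characteristics for its stopping rules, so there is no figure to reproduce. The check has two parts.

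**1. Apply the four triggers to each pair of events in one cohort** (both ARs unimproved at 14 days, neither serious):

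| Pair | Grade 2 count (needs 2) | Grade 3 count (needs 2) | Serious (needs 1) | Qualifying IRRs (needs 2) | Mandatory result |
|---|---|---|---|---|---|
| Two Grade 2 | 2 | 0 | 0 | 0 | Cohort and equal or higher doses stop |
| One Grade 2, one Grade 3 | 1 | 1 | 0 | at most 1 | None |
| Two Grade 3 | 0 | 2 | 0 | 0 to 2 | Study stops |

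The middle row holds even if both events are IRRs, because a non-serious Grade 2 IRR does not count towards the IRR trigger. Enumerating all mixes of these event types among the 6 active participants per cohort (Protocol Section 4.1), one plus one is the only mix whose result changes if the AR trigger counts Grade 2 or higher.

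**2. How often could it arise?** The documents give no AR rates, so every rate below is an assumption. Let

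- q2 = chance that a participant has a persistent Grade 2 AR,
- q3 = chance of a non-serious Grade 3 AR of any duration,
- f = share of those Grade 3 ARs unimproved at 14 days.

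With 6 active participants:

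- Mixed pair: P(N2 = 1, N3 = 1) = 30 × q2 × q3 × (1 − q2 − q3)^4
- Gap: f × that probability

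Worked case, q2 = 5%, q3 = 1%, f = 50%: 30 × 0.05 × 0.01 × 0.94^4 = 1.17%, and half of this is 0.59%.

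| q2 (with q3 = 1%) | Mixed pair | Gap, f = 25% | Gap, f = 50% | Stop as written | Stop if Grade 2 or higher, f = 50% |
|---|---|---|---|---|---|
| 2% | 0.53% | 0.13% | 0.27% | 0.71% | 0.98% |
| 5% | 1.17% | 0.29% | 0.59% | 3.42% | 4.01% |
| 10% | 1.88% | 0.47% | 0.94% | 11.56% | 12.51% |
| 20% | 2.34% | 0.58% | 1.17% | 34.58% | 35.75% |

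The stop columns are P(N2 ≥ 2 or N3 ≥ 2), with the gap added in the last. IRR and serious-AR triggers are left out. Over the same q2 and f, the gap is 0.07% to 0.60% at q3 = 0.5% and 0.25% to 2.22% at q3 = 2%. For given rates these are upper values, since an AR that passes from Grade 2 to Grade 3 may already be counted.

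The result is driven by the inputs. If every Grade 3 AR is taken as unimproved, the gap is 7.8% at q2 = 10%, q3 = 5%, and 14.4% at q2 = 20%, q3 = 10%. Nothing in the documents supports rates that high, or any other particular rate.

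**The case against.** **Grade 2 is plainly a minimum.** The analysis above takes two participants to mean at least two, so it can be called inconsistent to take Grade 2 as exactly Grade 2. If both are minimums, there is no gap. That is a fair account of how a sensible team might apply the rule. But the individual-level rule in the same section writes a minimum-grade sign where it means one, and Section 10.3.3 treats the grades as distinct. A mandatory stop should not depend on the reader supplying the sign.

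**A persistent Grade 3 AR would be serious.** Much of this stands. An incapacitating reaction unimproved for 14 days overlaps heavily with persistent disability, and it may also be serious through hospitalisation or as an important medical event (Section 10.3.2). One serious AR stops the study. Grade 4 and 5 events are serious by definition. A reader might infer that headache fills the gap, given the "100% incidence rate of headache" reported in Section 2.3.3 and the statement "This definition is not intended to include experiences of relatively minor medical significance such as uncomplicated headache". The documents do not support that. The exclusion qualifies only the disability criterion, and the earlier headaches were mild to moderate. What remains is mainly laboratory abnormalities, whose grade can rest on a number and not on incapacity (SAP Section 12.2), and a small clinical remainder.

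**Other controls cover it.** A reader might infer that the cohort would simply carry on. It need not:

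- the Grade 3 participant is discontinued;
- the Investigator and/or SRC decide on continuing or modifying dosing (Protocol Section 6.6);
- the second sub-cohort starts only after a documented Investigator decision on at least 7 days of multiple-dose safety data (3 days for single doses), and the SRC gates Cohorts 2, 4, 5 and 6 (Table 15);
- Grade 2 ARs are handled in consultation with the sponsor;
- Section 8 says "Immediate safety concerns should be discussed with Alexion immediately upon occurrence or awareness", and the termination grounds in Section 7.4 include "Discovery of an unexpected, serious, or unacceptable risk to participants enrolled in the study".

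The SRC charter is not among the documents, so a mid-cohort review cannot be excluded. These are real protections, but each acts on one participant, gates later dosing, or rests on judgement. None obliges the current cohort to stop.

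**Doses still to come.** If both ARs follow dose 1 and the 14 days run from that dose, the first sub-cohort at Day 15 has 10 of 12 doses left in Cohort 3, or 2 of 4 in Cohorts 4 to 6, counting that day's dose. A reader might take these as the exposure at risk. The protocol does not say which dose starts the clock. For a Grade 2 participant still dosed weekly it could be the latest one, and the counts would then not follow.

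**Conclusion.** The point holds on the literal wording. One persistent Grade 2 AR plus one unimproved, non-serious Grade 3 AR in the same cohort meets none of the four mandatory triggers, while two persistent Grade 2 ARs meet one. It is the only mix that the rule orders wrongly, and the clinical events that can fall into it are few.

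The frequency cannot be estimated from the documents. The figures above show scale under assumed rates and should not be quoted as risks for this trial. Nor do the documents show that participants would go unprotected, since judgement-based controls apply throughout. The defect is confined to the mandatory rule.

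Severity is minor, at the low end. SAP Section 4.1 records early termination, with 2 participants in Cohort 2 and none in Cohort 6, so the practical value now lies mainly in not carrying this wording into another protocol.

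**What to change.** In the cohort-level AR bullet, put a minimum sign on both the count and the grade, so that the trigger is *≥ 2 participants on study drug with a Grade 2 or higher AR not improved by 14 days after treatment*. This closes the gap and settles ARs that move from Grade 2 to Grade 3. The study-level bullets can stay as they are. A further rule for Grade 3 ARs that do improve is not needed to correct the ordering.

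The cost is a few words, with no extra data or participants, and slightly more cohort stops. At an assumed 1% Grade 3 rate the chance of an AR-based stop in a cohort rises by 0.13 to 1.2 percentage points, for example from 3.42% to 4.01% at q2 = 5% and f = 50%.
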